2 LIST OF ABBREVIATIONS AND DEFINITION OF TERMS

AE Adverse Event
CRF Case Report Form

FDA Food and Drug Administration

GCP Good Clinical Practice

GMP Good Manufacturing Practice IRB Institutional Review Board

ITT Intention To Treat

LOCF Last Operation Carried Forward MEC Medical Ethics Committee MITT Modified Intent-To-Treat MRI Magnetic Resonance Imaging

n Number

NaCl Sodium chloride NP Nucleus pulposus

OPDQ Oswestry Low Back Pain Disability Questionnaire

ODI Oswestry Disability Index

PP Per Protocol

PTT Partial thromboplastin time SAE Serious Adverse Event SAS Statistical analysis system

SF-36 Short Form 36

SOP Standard Operating Procedure

SUADE Serious Unanticipated Adverse Device Event

UADE Unanticipated Adverse Device Event

V Visit

VASPI Visual Analogue Scale of Pain Intensity

CONFIDENTIAL	Clinical Protocol	DATE	Р	age
		9Dec2019		
	mented Disc Regeneration in the $\underline{\mathbf{T}}$ reatment of th or without Intervertebral Disc Herniation –	WRITER TG, DB, PW	NO. 17	REV 6

3 OBJECTIVE

The objective of this study is to evaluate the safety and efficacy of viable allograft transplantation for the treatment of patients with symptomatic disc degeneration and tissue loss.

The primary criterion is the outcome of the Oswestry Low Back Pain Disability Questionnaire (OPDQ) modified according to Hudson-Cook and calculated as the Oswestry Disability Index (ODI) at 6 and 12 months after transplant, and the Visual Analogue Scale of Pain Intensity (VASPI) at 6, and 12 months following allograft supplementation. Secondary parameters of efficacy will include SF-36. Structural outcomes will be assessed using X-ray and Magnetic Resonance Image (MRI) measurements at 12 months. Safety will be assessed by the incidence and severity of adverse events (AEs) and clinically important changes in laboratory tests. All subjects (excluding conservative care crossover subjects) will be randomized to include MRI at 6-month follow-up (MRI or no MRI, ratio 1:1) in addition to all other assessments. Subjects randomized to conservative care will be assessed at 3 months. If at 3 months these subjects demonstrate a significant decline in condition, they will be offered the option to receive allograft treatment and will be followed for the subsequent 6 and 12 months. The conservative care subjects that crossover to the allograft treatment group will all receive an MRI at 6-month and 12-month follow-up after allograft treatment.

A correlation of the clinical results (scores) and the morphological results (X-ray, MRI) will be evaluated. All additional efficacy and safety data will be analyzed descriptively.

The optional long-term follow up will allow for additional objectives to be analyzed. At 24 and 36 months, subjects will have the opportunity to fill out VASPI, ODI, SF-36, and Resource Utilization forms which will be analyzed and compared to the original 12-month data. The active allograft and placebo cross over to allograft treatment at 24 months will also be asked to fill out the same questionnaires. This data will be compared to the first 12 months of data in the placebo group.

CONFIDENTIAL	Clinical Protocol	DATE 9Dec2019	P	age
	mented Disc Regeneration in the T reatment of th or without Intervertebral Disc Herniation –	WRITER TG, DB, PW	NO. 18	REV 6

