A variety of autologous ADRCs have been tested and are being utilized in a variety of indications in the clinic including breast reconstruction surgery subsequent to mastectomy, ^{43,44,45} cosmetic surgery of the face^{46,47} and breast, ⁴⁸ and both acute⁴⁹ and chronic⁵⁰ cardiovascular disease. While the mechanism of action remains to be fully elucidated, pre-clinical studies indicate that a variety of cells transplanted into the disc are capable of generating extracellular matrix and providing the necessary cellular components required to prevent further disc degeneration following discectomy. Cells aligned to this study and supplementary allograft material offer confidence in

CONFIDENTIAL	Clinical Protocol	DATE	Р	age
		9Dec2019		
	mented Disc Regeneration in the T reatment of th or without Intervertebral Disc Herniation –	WRITER TG, DB, PW	NO. 23	REV 6

differentiation towards a nucleus pulposus phenotype, therefore, it is warranted to conduct this study and to confirm this technology in a controlled, safe, and regulated environment.

To minimize patient risk, the first 24 patients (at least 4 from each group) will have an additional clinic visit one month after transplantation and will undergo a full safety assessment; including X-ray and MRI (see Appendix A). All data collected up to and including this point in the study will be collected and reviewed by the Steering Committee, who will determine if patient recruitment can continue. The parameters used by the Safety Committee to determine whether recruitment can continue, will be pre-defined in a separate document but will include the following:

- 1. A comparison of the adverse event (AE) profile between the three groups including rate, relationship, and severity.
- 2. A comparison of the clinical laboratory parameters between the three groups.
- 3. A comparison of vital signs and physical examination findings between the three groups.
- 4. A comparison of X-ray and MRI findings between the three groups.

CONFIDENTIAL	Clinical Protocol	DATE 9Dec2019	P	age
	mented Disc Regeneration in the $\underline{\mathbf{T}}$ reatment of th or without Intervertebral Disc Herniation –	WRITER TG, DB, PW	NO. 24	REV 6

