	mented Disc Regeneration in the $\underline{\mathbf{T}}$ reatment of th or without Intervertebral Disc Herniation –	WRITER TG, DB, PW	NO. 38	REV 6

- MRI evaluating the intervertebral height, adjacent endplates, deprivation of fluid and Pfirrmann score will be obtained during the Screening Phase and in the 2 weeks prior to transplant, and in the Active Phase at 12 months. Subjects will be randomized, yes or no (1:1 ratio), to receive an MRI at 6 months. Conservative care subjects that crossover to the allograft treatment group will all receive an MRI at 6-month follow-up after allograft treatment.
- X-rays will be performed static (standing), anterior-posterior and lateral in the Screening Phase prior to transplant. After transplantation, during the Active Phase (Months 6, and 12) a static and an additional dynamic (flexion/extension) X-rays will be performed.
- Adverse Events (AEs) and Serious Adverse Events (SAEs) will be recorded once the
 patient is enrolled (Day 0 of the Active Phase). A detailed discussion of AEs and SAEs is
 located in Section 14. Optional checkup evaluations will be performed in the case of
 complications. Failure of treatment defined as the necessity of a follow-up operation
 will be documented separately.
- Laboratory investigation will be conducted according to the routine procedures of each investigational center. The valid normal ranges including the methods for all parameters will be provided to the sponsor prior to the start of the study. Only laboratory values outside the normal range will be evaluated and commented upon by the investigator. The following parameters will be determined:

Hematology: Clinical Chemistry:

- hemoglobin - creatinine

- hematocrit - alkaline phosphatase

- erythrocytes - AST/SGOT - leukocytes - ALT/GPT - thrombocytes - γ -GT

- erythrocyte sedimentation rate - glucose

Coagulation:

- PTT

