9.3 Secondary Endpoints

Secondary parameters of efficacy will include the ODI, the SF-36, and the VASPI following treatment. Structural outcomes will be assessed using X-ray and MRI measurements at the same time points. Safety will be assessed by the incidence and severity of AEs and clinically important changes in laboratory tests.

A correlation of the clinical results (scores and scales) and the morphological results (X-ray, MRI) will be evaluated. All additional efficacy and safety data will be analyzed descriptively.

The effect supplemental allograft transplant on resource utilization, i.e., days off work, subsequent surgeries, other clinic visits will also be measured and compared

CONFIDENTIAL	Clinical Protocol	DATE	Р	age
		9Dec2019		T
TITLE: V iable A llograft S upplemented Disc Regeneration in the T reatment of Patients with Low Back Pain with or without Intervertebral Disc Herniation – VAST-001-017		WRITER TG, DB, PW	NO. 40	REV 6

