7 GENERAL ISSUES FOR STATISTICAL ANALYSIS

Data will be presented using descriptive statistics. Categorical data will be presented using frequencies and percent of subjects in each category. Continuous data will be presented using mean, standard deviation, median, minimum, maximum, and sample size.

Results will be generated by treatment group.

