9.2 SECONDARY ENDPOINTS

All secondary variables will be analyzed in an exploratory way, with no adjustment for multiple testing. The secondary endpoints include:

- Improvement in ODI and VASPI at 6 months
- Improvement in ODI, SF-36, and VASPI at 6 and 12 months after treatment
- MRI measurements at 6 and 12 months after treatment
- Adverse Event (AE)/ Serious Adverse Events (SAE) rates after treatment
- Hospitalization rate at 12 months after treatment
- Re-operation rate at 12 months after treatment
- Resource utilization following treatment at 6 and 12 months after treatment
- Changes in laboratory tests

Improvement in ODI, VASPI, and SF-36 will be analyzed similar to the primary endpoint, using the Kruskal-Wallis test to test for an overall difference between the three treatment groups. If the overall test is significant, the Dwass, Steel, Critchlow-Fligner Method will be used to asses all pairwise comparisons.

Adverse event rates, serious adverse events rates, hospitalization rates, and re-operation rate will be summarized by treatment group and compared using the chi-square test of independence or Fisher's exact test, as appropriate.

MRI data will be summarized by treatment group as mean at each timepoint, and mean change from baseline. Analyses will be done focusing on the level treated, but additional analyses will be completed which examine all five levels to see if there are adjacent level effects. Group comparisons will be made using the Krusal-Wallis test. If the overall test is significant, the Dwass, Steel, Critchlow-Fligner Method will be used to assess the pairwise comparisons.

Resource utilization and changes in laboratory tests will be summarized by treatment group.

10 Adverse Events

All adverse events will be coded using the standardized Medical Dictionary for Regulatory Activities (MedDRA) central coding dictionary, version 22.1 or greater.

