10.1 All Adverse Events

A summary of incidence rates of individual AEs by System Organ Class (SOC) and Preferred Term (PT) will be prepared. Because a subject may experience more than one AE, summaries will provide both the number of subjects experiencing at least one event and the number of events. Percentages provided will be the percent of subjects experiencing one or more adverse events.

A listing of all adverse events will be provided which includes subject number, AE number, days since procedure, AE SOC and PT, severity of AE, whether or not the AE is classified as serious (SAE), the relationship to investigational device, relationship to procedure, relationship to other etiology, the action taken, and the outcome.

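### Adverse event severity and clinically important laboratory changes are protocol safety criteria, but no table in the SAP's final analysis counts or compares either of them by arm

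*Protocol*

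**What the plan says.** **Safety criteria.** Protocol Section 3: "Safety will be assessed by the incidence and severity of adverse events (AEs) and clinically important changes in laboratory tests". Section 9.3 repeats it: "Safety will be assessed by the incidence and severity of AEs and clinically important changes in laboratory tests".

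**Laboratory analysis.** SAP 9.2: "Resource utilization and changes in laboratory tests will be summarized by treatment group". SAP 7 gives the general format: "Continuous data will be presented using mean, standard deviation, median, minimum, maximum, and sample size". The SAP text contains no definition of a clinically important change, no shift table, no count of abnormal values and no laboratory listing. Laboratory change is a secondary endpoint (SAP 3.2.2). SAP 9 assigns secondary variables to the mITT and PP populations, and SAP 6.2 analyses mITT as randomised.

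**Adverse event analysis.** SAP 10.1: "A summary of incidence rates of individual AEs by System Organ Class (SOC) and Preferred Term (PT) will be prepared". SAP 10.3 and 10.4 plan the same table for serious events and for treatment- or procedure-related events. In all three sections severity is only an item in the subject listing. SAP 6.4 makes the safety population, grouped by treatment received, primary for adverse events.

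**Source of laboratory values.** Under Protocol 8.5 laboratory work is to "be conducted according to the routine procedures of each investigational center". The same paragraph adds: "The valid normal ranges including the methods for all parameters will be provided to the sponsor prior to the start of the study". Investigators evaluate and comment on out-of-range values.

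**The concern.** The protocol names three things to judge safety by: how often adverse events occur, how severe they are, and whether laboratory values change in a clinically important way. The SAP tabulates the first. The other two have no by-arm count or comparison in the final analysis, and SAP Section 13, which records other departures from the protocol, mentions neither. This looks like an omission rather than a decision.

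It matters because the protocol says there are no clinical data for this product in this population (Section 12) and lists immunological, inflammatory and infectious events among the expected risks (Section 14.1). Harms of that kind could plausibly appear as large changes in a few subjects. The panel includes erythrocyte sedimentation rate and leukocytes, but a mean or median is a poor instrument for a few large changes. For severity, a table by System Organ Class and Preferred Term looks the same whether the events in an arm were mild or severe.

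**Working it through.** The documents give no safety event rate, threshold or power, so there is no plan figure to reproduce. The check sets the texts side by side and then sizes the laboratory gap with assumed inputs.

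**1. Criterion against output**

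- Incidence of adverse events: tabulated by System Organ Class and Preferred Term (SAP 10.1, 10.3, 10.4), and rates are tested (SAP 9.2). Met.
- Severity: a listing item only (SAP 10.1, 10.3, 10.4). Seriousness has its own table, but seriousness is not severity. Not tabulated by arm.
- Clinically important laboratory changes: a group summary (SAP 9.2 with SAP 7), with no criterion and no count. Not tabulated by arm. By contrast, SAP 8.4 does plan normal/abnormal counts for the baseline physical examination.

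**2. What the continuous summary would show (assumed inputs)**

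Arm sizes are 140 allograft and 40 saline (SAP 4). Suppose k allograft subjects shift by s standard deviations on one test and nobody else changes.

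- Mean shift = k × s / 140. For k = 3 and s = 5: 15/140 = 0.107 SD.
- Standard error of the allograft-saline difference = √(1/140 + 1/40) = 0.179 SD. Ratio: 0.107/0.179 = 0.60.
- Allowing for the spread that the outliers add: with f = 3/140, the allograft SD becomes √(1 + f(1 − f) × 25) = 1.23. The standard error becomes √(1.524/140 + 1/40) = 0.189, and the ratio 0.57.
- Over k = 1, 2, 3, 5 and s = 3, 5, 10, using the simple standard error, the ratio runs from 0.12 to 1.99. It is at or below about 1 in 10 of the 12 combinations.
- The median hardly moves.

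**3. What the planned minimum, maximum and SD add**

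The expected maximum of 140 standard normal values is about 2.63 SD (simulated), so a 5 SD value would stand out, and the SD would rise from 1.00 to 1.23. These figures signal that something extreme occurred. They do not give the number of subjects affected, or whether a value is abnormal for the site that measured it. With up to 20 sites, differences in local methods could also widen the range.

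**4. What a count adds**

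The same data would read 3/140 (2.1%) against 0/40. Fisher's exact test gives p = 1.00 against 0/40, and p = 0.56 against 0/80 (saline and conservative care together). Among the counts tried against 0/40, 10/140 gives p = 0.12 and 14/140 gives p = 0.042. The gain is therefore in description, not in inference.

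**5. Grouping of crossover subjects**

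Conservative-care subjects may receive allograft after Month 3 (Protocol 7.1.4). Under SAP 9 with 6.2, their laboratory changes after allograft stay under conservative care, while adverse events follow treatment received (SAP 6.4). The two halves of the safety assessment would then group the same subjects differently.

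**The case against.** A reader might infer that a small cluster of harmed subjects would go unseen. The documents do not support that. SAP 7 plans the minimum, maximum and SD as well as the mean and median. Infection and inflammatory response are expected adverse events, so they would be counted by Preferred Term. Serious events, related events and events leading to withdrawal have their own tables (SAP 10.2 to 10.4). Rates of adverse events, serious events, hospitalisation and re-operation are compared by test (SAP 9.2). Every adverse event is listed with its severity, and Protocol 13.1.2 requires listings of all analysed data.

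A reader might also infer that pooling local laboratories makes the summaries meaningless. That goes too far: the endpoint is change, and a within-subject change removes a constant offset between laboratories if the same laboratory is used each time. Differences of scale remain.

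Nor are these criteria never compared. For the first 24 subjects at Month 1, Protocol Section 5 requires "A comparison of the adverse event (AE) profile between the three groups including rate, relationship, and severity" and a comparison of laboratory parameters. But this early review covers 24 of 220 subjects (10.9%) and does not replace the final analysis.

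Finally, SAP 9.2 does not forbid abnormality counts, SAP 7 has a format for categorical data, and SAP 12 defers reporting standards to a procedure that was not supplied. For laboratory data the SAP could therefore be called under-specified rather than contrary to the protocol. That argument is weaker for severity, because SAP 10 names its tables and none has a severity dimension.

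**Conclusion.** The gap is real and moderate in size. Two of the protocol's stated safety criteria are not counted or compared by arm in the final analysis, and the SAP does not say that they were dropped. Individual extreme values and severe events would still be visible, so the accurate conclusion is that such harms are left unquantified between arms, not that they are hidden.

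The textual mismatch rests on the documents alone. The size of the laboratory effect rests on assumed cluster sizes and shifts, and on normally distributed changes for the expected maximum. With 140/40/40 subjects the benefit of the missing tables is descriptive, which fits the protocol's statement that additional safety data are analysed descriptively. How the case report form codes severity and laboratory comments could not be checked. Protocol Section 14 gives no severity scale, although the SAP listings presuppose a severity grade.

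**What to change.** **SAP 10.** Add a by-arm table of subjects by worst adverse event severity, for all events and for related events, in the safety population. State the severity scale used.

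**SAP 9.2.** Keep the continuous summary and add:

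- Shift tables by arm (low, normal or high against each site's own range) from baseline to Month 6 and to Month 12. These visits are common to all arms. Do not use the worst post-baseline value: Appendix A gives conservative care an extra Month 3 draw, hence more chances of an abnormal result.
- The number and percent of subjects with a clinically important change, using a criterion fixed before database lock, or the investigator's comment if the case report form codes it.

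**Population.** Run the laboratory tables in the safety population by treatment received (SAP 6.4) instead of mITT and PP. For crossover subjects, count values before allograft under conservative care and values after it under allograft, against the new baseline defined in Protocol 7.1.4. State the denominators, because such a subject contributes to both groups.

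**Cost.** A few extra tables, some SAP wording, and programming to apply site-specific ranges. The ranges already go to the sponsor, and severity is already planned for the listings. Whether the count of clinically important changes needs any further coding depends on the case report form.
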